7.2.2 Radiographic evaluation

Patients will be removed from study if they have evidence of radiographic disease progression as defined below. Radiographic analysis via CT scan (and/or MRI), and bone scan will occur at baseline, 6 months, and 12 months. For the purposes of this study, investigators should utilize the protocol-specified tumor assessment criteria, defined as assessment of evaluable soft tissue disease sites according to RECIST v1.1, and/or assessment of bone disease according to the PCWG2 criteria. Soft tissue disease will be assessed on CT (or MRI) and defined by RECIST v1.1. Bone disease will be assessed on bone scan and progression will be defined as the development of two or more new bone lesions from baseline confirmed with an additional lesion on bone scan 6 weeks later. New bone lesions noted after the 6-month radiographic assessment do not require a confirmatory bone scan. Increase in intensity of known bone lesions will not constitute progression. The date of progression will be recorded as the date the first scan shows change.

7.3 Body composition evaluation

The change in bone health will be assessed via urine N-telopeptide and serum bone specific alkaline phosphatase measurements. Bone density will be assessed via a DXA scan. The density of the posterior-anterior lumbar spine, total hip, femoral neck, and total body bone mineral density will be analyzed. Additional body composition analysis of lean body mass and total body mass will be analyzed via cross sectional CT image analysis. Changes in body composition can be seen as early as 3 months in studies of testosterone supplementation ³⁹ or ADT ⁴⁰ causing an increase in adipose tissue and decrease in lean muscle.

7.4 Quality of life assessment

The Functional Assessment of Cancer Therapy – Prostate (FACT-P) questionnaire will provide data on how patients perceive their QOL while on enzalutamide or ADT. The FACT-P tests five subscales: physical, social, emotional, functional wellbeing and additional concerns specific to men with prostate cancer ⁴¹. The FACT-P scales have been widely used to evaluate quality of life in clinical trials for prostate cancer treatments. Internal consistency of the FACT-P (version 4) subscales ranges from 0.85 to 0.89. Concurrent, construct and discriminant validity has been documented (41). The FACT-P will be used descriptively. The questionnaire must be administered at each study visit unless the patient refuses. It is permissible to assist the patient with the completion of the questionnaire. The study staff must review the questionnaire at each visit in order to ensure that all items were answered. Patients should be given the option to complete any unmarked questions, but it is not required.

The Sexual Health Inventory for Men (SHIM) will also be used to evaluate alterations in sexual health as a result of treatment with enzalutamide or ADT. The SHIM is a scale used widely to assess the presence and severity of erectile dysfunction. The scale is used regularly in clinical practice as well as in the research setting. The SHIM will be used descriptively. The questionnaire must be administered at each study visit unless the patient refuses. It is permissible to assist the patient with the completion of the questionnaire. The study staff must review the questionnaire at each visit in order to ensure that all items were answered. Patients should be given the option to complete any unmarked questions, but it is not required.

7.5 Physical function evaluation

The Short Physical Performance Battery (SPPB) will be used for physical function evaluation. This battery of tests evaluates physical function and mobility. The test includes assessment of a patient's ability to perform a chair rise, standing balance, and a 8 foot walk. This battery has a clear scoring system and a validated score above which patients are identified as at-risk of physical decline. Change in score of 1 is clinically significant. The SPPB will be modified to include a 10-time chair rise. The coordinator will record the time it takes the subject to perform both 5 and 10 rises from the chair. This modification has been made to increase the sensitivity of the exam in identifying small changes in function given the generally fit population seen in the clinic.

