3.2 Secondary Endpoints

- Incidence of metabolic syndrome within 6 months, as defined by the ATP III, in patients treated with enzalutamide versus patients treated with standard testosterone-lowering ADT
- Change in bone density, as measured by a DXA scanner
- Change in bone turnover as measured by bone-specific alkaline phosphatase and N-telopeptide
- Change in body composition (fat distribution as measured on CT)
- Change in QOL, as measured by the FACT-P and SHIM
- Time to PSA progression and time to radiographic progression. Progression will be defined as lack of clinical benefit in the setting of either rising PSA, growth of visceral or soft tissue metastasis, or development of new bone metastasis as defined per protocol
- Incidence of developing individual risk factors, or components, which comprise metabolic syndrome
- Change in inflammatory markers as measured by serum hs-CRP

- Safety and tolerability as assessed by regular recording of toxicities via physical exam and laboratory analysis using the CTCAE v4.1 guidelines
- Change in physical function as measured by the Short Physical Performance Battery

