10.1.1 Endpoint Analysis

Primary endpoint

Metabolic syndrome incidence will be summarized by the proportion of patients with at least 3 of the 5 pre-specified criteria within the first 12 months of therapy.

Secondary endpoint

The secondary endpoints will be presented as follows:

Metabolic syndrome incidence will be summarized by the proportion of patients acquiring with at least 3 of the 5 pre-specified criteria within the first 6 months of therapy.

The change in bone turnover markers from baseline will be assessed for each treatment group. Measurements will be taken at day 1 of each cycle and reported as a continuous variable. A paired t-test will test within an arm as to whether the change from baseline to each time point is significantly different from zero.

The change in bone density, free fat mass, and fat mass will be measured at baseline, 3 months and 12 months and assessed for each treatment group. A paired t-test will test within an arm as to whether the change from baseline to each time point is significantly different from zero.

The change in QOL scores as measured by the FACT-P and SHIM at each visit, will be assessed in each treatment group.

Median time to PSA progression as defined in section 7.2. Time to PSA progression is defined as the time from randomization to the earliest objective evidence of PSA progression as defined per

protocol. If a patient has had a decline in PSA while on study, the PSA progression date is defined as the time from documented PSA nadir to an increase in PSA with confirmation as defined by protocol. Time to radiographic progression is defined as the time from randomization to the earliest objective evidence of radiographic progression as defined per protocol. Patients will be monitored at regular intervals for PSA change and radiographic change. Log rank test will be used to compare the distributions of above variables between the group treated with enzalutamide to the group on standard ADT.

The change in markers of inflammation as measured by circulating hs-CRP will be obtained at the beginning of each cycle.

Adverse events data will be summarized using tables and descriptive statistics.

The change in SPPB from baseline to 12 months will be measured as a continuous outcome. A clinically relevant change is a change in total score of 1, with a standard deviation at baseline of 1.5⁴².

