Mean, standard deviation, median, and range will be reported for each outcome at each time point, and the mean and standard deviation of the changes, will be calculated. One-group t-test will be used to estimate effect size of each outcome measure and test if the change is significant at 0.05 significance level. Pearson or Spearman correlation coefficients will be used to assess the association between continuous variables.

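### The chair-rise times are recorded to make the physical-function test more sensitive, but no endpoint or analysis names them, and the SPPB change gets no between-arm estimate

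*Combined protocol and SAP*

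**What the plan says.** - **Assessment (7.5).** "The SPPB will be modified to include a 10-time chair rise", and "The coordinator will record the time it takes the subject to perform both 5 and 10 rises from the chair". The reason given is to "increase the sensitivity of the exam in identifying small changes in function given the generally fit population seen in the clinic". The same section keeps a threshold on the score: "Change in score of 1 is clinically significant".
- **Timing (Table 1 and 6.3.2).** The battery is done at Months 1, 4, 7, 10 and 13.
- **Objective and endpoint (2.2, 3.2).** The secondary objectives are introduced as a comparison of enzalutamide with traditional ADT. The endpoint reads: "Change in physical function as measured by the Short Physical Performance Battery". Neither place mentions a rise time.
- **Analysis (10.1.1).** "The change in SPPB from baseline to 12 months will be measured as a continuous outcome". The next sentence puts the relevant change at 1 point on the total score and the baseline SD at 1.5, citing a pilot trial of physical activity in elders. General text at the end of the section promises descriptive statistics for each outcome at each time point and adds: "One-group t-test will be used to estimate effect size of each outcome measure and test if the change is significant at 0.05 significance level".
- **Appendix 16.3 (SPPB).** It is listed in the table of contents. Its text was not available for this review.

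**The concern.** There are two gaps, both in how the physical-function objective is carried into the analysis.

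First, a measurement was added for a stated purpose, and the places that define what will be analysed do not mention it. Someone following 3.2 and 10.1.1 could complete the SPPB analysis without tabulating a rise time. Someone else could look at the total score, the 5-rise time and the 10-rise time and decide afterwards which to present. In an open-label trial that choice should be fixed beforehand.

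Second, Section 1.4 sets out to evaluate enzalutamide versus ADT on physical function, among other outcomes, but a one-group test asks only whether a mean change differs from zero. Two such tests, one per arm, do not estimate the difference between arms. One arm may reach significance and the other may not even when both lose the same amount.

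At stake is a clear answer on one of the ADT harms that Section 1.2 uses to motivate the trial.

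**Working it through.** **1. Tracing the rise times through the plan**

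| Place | SPPB named? | Rise time named? | Contrast between arms named? |
|---|---|---|---|
| 2.2 objective | yes | no | yes (introductory line) |
| 3.2 endpoint | yes | no | no |
| 7.5 assessment | yes, modified | yes, 5 and 10 rises | no |
| 10.1.1 SPPB sentences | yes; relevance on total score | no | no |
| 10.1.1 general text | each outcome | no | no (one-group t-test) |

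Within 10.1.1 the log-rank test for the two progression endpoints is stated to compare the arms. No such statement is made for SPPB.

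**2. Two readings of the SPPB endpoint**

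- If the 10-rise is not scored, the endpoint is the standard total and the added timing has no stated analysis.
- If the 10-rise is scored, the available text gives no scoring rule, and nothing shows that the 1-point threshold and SD of 1.5 carry over to an altered score.

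Either way, 3.2 and 10.1.1 need a sentence.

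**3. Volume of data**

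56 men × 5 visits = 280 batteries at most, each with both rise times.

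**4. What the total score could show**

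The plan gives no power for SPPB, so there is no figure to reproduce for this endpoint. (The primary design does reproduce: exact enumeration for 28 per arm, 7% vs 32%, gives power 81.1% and alpha 0.0538, against the stated 80% and 0.054.)

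Inputs from 10.1: n = 28 per arm. Inputs from 10.1.1: difference 1 point, SD 1.5. Assumptions: the SD is also 1.5 at 12 months; the correlation r between baseline and 12 months is 0.5, range 0 to 0.8; tests are two-sided at 0.05; no man is lost.

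- SD of change = 1.5 × √(2(1 − r)). This is 1.5 at r = 0.5, 2.12 at r = 0 and 0.95 at r = 0.8.
- *One arm, 1-point change from baseline.* Noncentrality = √28 / 1.5 = 3.53 on 27 df, so power is 92.5% (67% at r = 0, over 99% at r = 0.8).
- *Between arms, 1-point difference in change.* SE = 1.5 × √(2/28) = 0.401. Power = Φ(1/0.401 − 1.96) = Φ(0.534) = 70% (42% to 98%). For 80% power, n = 2 × (1.96 + 0.84)² × 1.5² / 1² ≈ 35.3, that is 36 per arm.
- *Between arms, adjusted for baseline.* Residual SD = 1.5 × √(1 − r²) = 1.30 at r = 0.5. SE = 1.30 × √(2/28) = 0.347. Power = Φ(1/0.347 − 1.96) = Φ(0.92) = 82% (70% at r = 0, 99% at r = 0.8).

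**5. Why two one-group tests are not a comparison**

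Suppose both arms truly lose 1 point, so there is no difference between them. The chance that exactly one of the two tests is significant is 2 × power × (1 − power) = 2 × 0.925 × 0.075 = 14% at r = 0.5, and 2 × 0.672 × 0.328 = 44% at r = 0.

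Nothing comparable can be computed for the rise time, because the documents give neither an SD nor a minimal important difference for it.

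**The case against.** The strongest reply is that 7.5 modifies the battery itself, so SPPB in 3.2 and 10.1.1 may mean the modified battery, with a scoring rule in Appendix 16.3. That stands as a possibility: the total score is mentioned only in the sentence on relevance, and an appendix that was not available cannot be counted as missing. It does not close the point, because the endpoint and analysis sections would still name no rise-time outcome and no contrast between arms.

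A second reply is that the general text covers each outcome, and a recorded time might count as one. It might, but no list of outcomes includes it. A reader might therefore infer that the times will never be used; the documents do not establish that. They leave the use unstated.

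A reader might also infer that the protocol regards the standard battery as too coarse for these men. It does not say so. It says the addition increases sensitivity, and it still treats a 1-point change as clinically significant. Nor can a ceiling effect be sized: no score distribution is given, and eligibility admits ECOG 2 and metastatic disease, so clustering at the top is plausible but not shown.

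Finally, this is one of ten secondary endpoints in a 56-patient phase II trial. That limits the weight of the point, and the remedy is correspondingly small.

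**Conclusion.** The point holds as an omission with two parts. The rise times recorded to add sensitivity have no named outcome or analysis in the available text, and the physical-function objective, which is comparative, reaches only a one-group test. Whether the 10-rise contributes to the score is unresolved without Appendix 16.3.

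The size is moderate. Up to 280 batteries are affected. For the total score, under the assumptions above, a baseline-adjusted contrast would have about 82% power for a 1-point difference (70% to 99% for r from 0 to 0.8), with a 95% CI of about ±0.68 points at r = 0.5 (1.96 × 0.347). The missing comparison is therefore feasible at the planned size, although dropout would reduce these figures. No gain in sensitivity from the rise time can be quantified from the documents. The primary endpoint, sample size and safety analyses are not affected.

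**What to change.** In 3.2 and 10.1.1:

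- Add change in 10-rise time (seconds), with 5-rise time as support, as a named supportive physical-function outcome alongside the SPPB total score.
- For both the total score and the 10-rise time, report the enzalutamide-minus-ADT difference in change from baseline to 12 months with a 95% CI, adjusted for the baseline value.
- Report the share of men at the maximum SPPB score at baseline, so that a reader can judge any ceiling.
- State that the 1-point threshold applies to the standard total score. If Appendix 16.3 scores the 10-rise, give that rule and report the standard total as well.

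The cost is a few sentences and one table, since the times are already collected. The downside is one more secondary analysis. The rise time has no stated minimal important difference, so it has to be interpreted by its confidence interval.

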7.6 Safety evaluations

The principal investigator will oversee the care and safety of all subjects enrolled in the trial. Study visits will include monitoring and recording all adverse events and serious adverse events; regular monitoring of hematology, blood chemistry, hepatic function; regular measurement of vital signs, physical examination including weight and performance status. Safety and tolerability will be assessed using the CTCAE v4.1 guidelines.

7.6.1 Adverse Events

Monitoring of AEs will be conducted throughout the study. AEs will be reported from the date written informed consent is obtained and through 30 days post-last dose of study drug. Serious pretreatment events and serious adverse events (SAE) will be reported to the Astellas, Inc. designee. All SAEs will be monitored until they are resolved or are clearly determined to be due to a patient's stable or chronic condition or intercurrent illness (es).

7.6.2 Clinical Laboratory Evaluations

Clinical laboratory evaluations will be performed locally. Chemistry and hematology results must be drawn and reviewed within 24 hours prior to each cycle of dosing.

7.7 Concomitant Medication and Therapies

Concomitant Strong CYP2C8 Inhibitors

The concomitant use of strong CYP2C8 inhibitors (i.e. gemfibrozil) should be avoided if possible as this increases the plasma AUC of enzalutamide and its active metabolite. If patients must be co-administered a strong CYP2C8 inhibitor, reduce the enzalutamide dose to 80 mg once daily. The enzalutamide dose should be readjusted if the inhibitor is discontinued.

The effects of CYP2C8 inducers on the pharmacokinetics of enzalutamide have not been evaluated *in vivo*. Co-administration of enzalutamide with strong or moderate CYP2C8 inducers (e.g., rifampin) may alter the plasma exposure of enzalutamide and should be avoided if possible.

Drugs that Inhibit or Induce CYP3A4

Co-administration of a strong CYP3A4 inhibitor increased the AUC of enzalutamide and its active metabolite by 1.3 times.

Co-administration of enzalutamide with strong CYP3A4 inducers (e.g., carbamazepine, phenobarbital, phenytoin, rifabutin, rifampin, rifapentine) may decrease the plasma exposure of enzalutamide and should be avoided if possible. Moderate CYP3A4 inducers (e.g., bosentan, efavirenz, etravirine, modafinil, naftilin) and St. John's Wort may also reduce the plasma exposure of enzalutamide and should be avoided if possible.

The following medications and procedures are PROHIBITED during the study:

- Any anti-cancer therapies other than enzalutamide or single agent ADT. Anti-androgens used during the initiation of ADT to avoid a flare phenomenon are acceptable for up to 4 weeks.
- Patients not on osteoclast inhibitors at study enrollment may not begin this treatment while on trial.

The following medications and procedures are ALLOWED during the study:

- Any supportive medications to treat the symptoms of enzalutamide or ADT are allowed such as agents to manage hot flashes, nausea, diarrhea, or depression

- Palliative radiotherapy, for treatment of the patient's malignancy. Patients with a fracture in an area of pre-existing metastasis without clear progression, the patient may remain on trial if approved by the PI.
- Anti-androgens used during the initiation of ADT to avoid a flare phenomenon are acceptable for up to 4 weeks.

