4.3 Overview of treatment

During the trial, patients will be assigned to treatment with either enzalutamide or standard of care ADT. For patients randomized to the ADT arm, the choice of type of ADT will be at the discretion of the treating provider. Patients that are in the enzalutamide arm may not also be treated with ADT. In addition, patients on the ADT arm may not also be treated with an androgen-receptor blocker. Anti-androgen therapy may be administered as a single agent \leq 14 days prior to and 14 days following medical castration with a GnRH agonist in order to cover the potential testosterone surge. Intermittent dosing of ADT is not acceptable. Enzalutamide will be dosed at the approved dose of 160mg orally daily. ADT will be administered according to the standard prescribing information for the agent. All subjects should also take at least 1000mg of calcium and 800 International Units (IU) of vitamin D. This treatment will allow protection against bone density loss caused by metastasis or ADT. All subjects will receive this treatment to avoid confounding data, as it is a non-toxic, non-prescription supplement.

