10.4 Secondary endpoint population

Defined as patients who have received at least 1 dose of either drug, have baseline values and at least 1 post-baseline assessment.

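### Bone endpoints get only within-arm tests, so the enzalutamide-versus-ADT objective is not tested, and existing osteoclast-inhibitor users are pooled with non-users

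*Combined protocol and SAP*

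**What the plan says.** Section 2.2 lists bone health among the objectives under a lead-in that contrasts enzalutamide with traditional ADT. Section 3.2 names bone density by DXA, N-telopeptide and bone-specific alkaline phosphatase as secondary endpoints.

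Section 10.1.1 gives the analysis. For turnover: "The change in bone turnover markers from baseline will be assessed for each treatment group". For density: "The change in bone density, free fat mass, and fat mass will be measured at baseline, 3 months and 12 months". The test for both is: "A paired t-test will test within an arm as to whether the change from baseline to each time point is significantly different from zero". The closing paragraph of 10.1.1 adds a one-group t-test to estimate effect size and "test if the change is significant at 0.05 significance level". No between-arm test, covariate or subgroup is given for bone. For PSA and radiographic progression, the same section does name a log-rank comparison of the two arms.

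On osteoclast inhibitors, section 7.7 says "Patients not on osteoclast inhibitors at study enrollment may not begin this treatment while on trial". The exclusion criteria in 5.2 do not mention these drugs. The secondary endpoint population in 10.4 does not remove users: "Defined as patients who have received at least 1 dose of either drug, have baseline values and at least 1 post-baseline assessment". Section 4.1 stratifies the 1:1 randomisation of 56 patients by metastasis only. Concomitant medications are recorded from screening onward (6.3.2) and coded (section 11), but no section links them to the bone analyses. For calcium and vitamin D, section 4.3 states: "All subjects will receive this treatment to avoid confounding data".

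**The concern.** There are two linked gaps, and the first is the larger.

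First, a test of whether each arm's mean change differs from zero does not compare the arms. One arm can be significant and the other not while the difference between them is small, and both can be significant while they differ. The randomisation is not used, and the question in 2.2 has no planned estimate, confidence interval or test.

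Second, osteoclast inhibitors act on the quantities being measured. Taking change from baseline removes a user's stable starting level, but not a different rate of change while on the drug. If users lose less bone than non-users, the within-arm mean is pulled towards zero. In an arm comparison, the mixture adds variance, and with 28 per arm the users may by chance fall unevenly.

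At stake is how readable one secondary objective will be. The metabolic syndrome endpoint does not depend on any of this.

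**Working it through.** **The plan's own figure.** The only sample-size figure is for the primary endpoint: 28 per arm, 7% versus 32%, one-sided chi-square, 80% power, actual alpha 0.054 (section 10.1). Exact enumeration of the uncorrected pooled test gives power 81.1% and size 0.0538 at the pooled rate of 19.5%, so the figure reproduces. It says nothing about bone: the documents give no SD, effect size or power for any bone endpoint.

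**Inputs.** From the documents: n = 28 per arm and a 0.05 level for change outcomes. Sidedness is not stated for those outcomes; two-sided is assumed here. Assumed, because the documents are silent: share of baseline users q = 5%, 10% or 20%; user minus non-user difference in percent change in bone density D = 3 or 6 points; residual SD = 3 points. Stratification is ignored.

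**(a) Dilution of the planned within-arm test.** Take a standardised change d that has 80% power at n = 28 (normal approximation): d = (1.960 + 0.842)/√28 = 0.529. If users show no mean change (assumed), the arm mean becomes (1−q)d and the SD becomes √(1 + q(1−q)d²). Power is Φ(mean × √28 / SD − 1.960).
- q = 5%: mean 0.503, SD 1.007, power about 75%.
- q = 10%: mean 0.477, SD 1.013, power about 70%.
- q = 20%: mean 0.424, SD 1.022, power about 59%.

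**(b) Chance imbalance between arms.** The numbers of users in the two arms are taken as independent binomials (28, q). A gap of 10 percentage points or more means at least 3 users, since 3/28 = 10.7% and 2/28 = 7.1%. The exact probability of a gap of 3 or more is 11.8%, 25.8% and 40.1% for q = 5%, 10% and 20%. A normal approximation with SD √(2q(1−q)/28) = 5.8, 8.0 and 10.7 points gives about 9%, 21% and 35%. That is too low, because the counts are small and discrete.

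**(c) What such a gap would do.** A 3-user gap shifts the arm difference by (3/28)D, which is 0.32 points for D = 3 and 0.64 for D = 6. The residual standard error of the arm difference is 3 × √(2/28) = 0.80. The shift is therefore about 0.4 to 0.8 of a standard error.

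**(d) What adjustment would gain.** Mixing users and non-users raises the variance from 9 to 9 + q(1−q)D². The proportional cut in standard error from adjusting is 1 − √(9/(9 + q(1−q)D²)).
- q = 5%: added variance 0.43 to 1.71, cut 2% to 8%.
- q = 10%: added variance 0.81 to 3.24, cut 4% to 14%.
- q = 20%: added variance 1.44 to 5.76, cut 7% to 22%.

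This ignores the lost degree of freedom and any further gain from adjusting for the baseline value.

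**The case against.** A reader might infer that unadjusted osteoclast-inhibitor use biases the trial's bone results. The documents do not support that. No between-arm bone test is planned, so there is no planned contrast for an imbalance to shift. If the arms were compared, baseline use precedes treatment, so randomisation keeps the unadjusted contrast unbiased in expectation, and its standard error already carries the user/non-user variation. Pooling gives the average effect in the eligible population, which is a legitimate quantity. Adjustment mainly buys precision and protection against a chance imbalance.

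A reader might also infer that the within-arm changes fail to estimate a treatment effect because of the users. They would fail to do so with no users at all, because there is no control comparison.

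Some handling already exists. The ban on new starts removes the post-randomisation source of use. Stratifying by metastasis may balance use given for bone metastases, though not use for other reasons. Medication records allow use to be described by arm. Section 7.7 gives no reason for the ban, and the confounding remark in 4.3 concerns calcium and vitamin D only, so the plan's intent about osteoclast inhibitors is an inference.

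Finally, every input that drives the size in (a) to (d) is assumed. At 5% there would be about 3 users among 56 patients, and the covariate would matter little.

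All of this stands, and it limits the second gap to precision and interpretability. It does not touch the first: the objective compares arms and the analysis does not.

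**Conclusion.** The point holds in a limited form. Section 10.1.1 leaves the arm comparison in 2.2 without an analysis for bone density and turnover; this follows from the text and needs no assumption. That existing users may continue and are pooled with non-users also follows from 7.7, 5.2, 10.4 and 10.1.1 read together.

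The effect of that pooling cannot be sized from the documents. The ranges in the working, from near negligible to a standard error cut of about 22%, are illustrations; the upper end needs both 20% users and a 6-point user effect. This is a desirable improvement to a secondary analysis, with low confidence in its size and no bearing on the primary endpoint.

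**What to change.** In section 10.1.1:
- Make the main analysis of bone density, N-telopeptide and bone-specific alkaline phosphatase a between-arm ANCOVA of change at each time point. Use baseline value and baseline osteoclast-inhibitor use (yes/no, from the screening medication list) as covariates, and report the adjusted arm difference with its confidence interval.
- Repeat it in non-users as a sensitivity analysis. The covariate deals with noise and chance imbalance; only this second analysis shows the arm difference free of any dilution by users.
- Tabulate baseline use by arm, and keep the within-arm changes as descriptive.

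The cost is analysis wording. The data are already collected, and no visit, treatment rule or sample size changes. The use covariate takes one degree of freedom and gains little if users are few; the non-user analysis is somewhat smaller.
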